### Adverse Events:

Unsolicited AEs are coded into Medical Dictionary for Regulatory Activities (MedDRA) preferred terms. The number and percentages of subjects experiencing each specific AE will be tabulated by severity and relationship to treatment. For the calculations in these tables, each subject's adverse experience will be counted once under the maximum severity or strongest recorded causal relationship to treatment.

A complete listing of adverse experiences for each subject will provide details including severity, relationship to treatment type, onset, duration and outcome.

### Local laboratory values:

Boxplots of local laboratory values will be generated for baseline values and for values measured during the course of the study. Each boxplot will show the 1st quartile, the median, and the 3rd quartile. Outliers, or values outside the boxplot, will also be plotted. If appropriate, horizontal lines representing boundaries for abnormal values will be plotted.

## **6.4.4 Tolerability Evaluation**

The tolerability of the medical product represents the degree to which overt adverse effects can be tolerated by the subject [23]. VRC 608 is the first trial of MAb114 in healthy adults. The tolerability evaluation will be mostly descriptive by nature and consist of solicited AEs that occur during the 3 days following MAb114 administration and reasons for any withdrawal or discontinuation based upon subject discomfort. This early assessment of tolerability of MAb114 will inform which parameters should be solicited or routinely assessed to further characterize the tolerability profile in a larger number of subjects.

## **6.4.5 Pharmacokinetics Analysis**

Blood samples for PK evaluations will be collected at timepoints per the Schedule of Evaluations.

**Individual Subject PK Analysis:** A non-compartmental PK analysis will be performed using Phoenix (Centara) or a similar program on the MAb114 concentration data generated from each subject. Calculated PK parameters for all groups will include: area-under-the-curve (AUC), maximum concentration (Cmax), time to Cmax (Tmax), clearance (CL), volume of distribution (Vd), terminal elimination rate constant ( $\lambda_z$ ) and the terminal half-life (T1/2). Cmax and Tmax will be taken directly from the observed concentration-time data. The terminal slope,  $\lambda_z$ , will be determined from the log-linear portion of the curve and the T1/2 calculated as 0.693/ $\lambda_z$ . AUC0-Clast will be determined using the linear trapezoidal method, where Clast is the concentration at 24 weeks after the dose. If the final sample (Clast) has measurable MAb114 concentrations, the remaining AUC after the final concentration (AUCClast-inf) will be estimated as Clast/ $\lambda_z$ . Data will be summarized by dose group.

**Population PK Analyses:** Population PK analyses will be performed on the MAb114 PK data following IV administration to determine compartmental PK parameters using the program NONMEM. One and two compartment PK models will be assessed. Based on prior PK studies of antibodies, it is anticipated that a two-compartment model will adequately characterize the data. The population analysis will generate estimates for initial and final volumes of distribution (Vd1 and Vd2), inter-compartmental clearance (Q), CL and bioavailability (F). Volume of distribution at steady-state (Vdss) will be calculated as the sum of Vd1 + Vd2. Given the small subject numbers, the population PK analysis will not include an exploratory covariate analysis to assess clinical

factors as fixed effects associated with MAb114 PK parameters with the exception of dose (5 vs 25 vs 50 mg/kg) as fixed effects on CL and  $V_{d_{ss}}$ . The terminal half-life,  $t_{1/2\beta}$  will be determined from CL,  $V_{d1}$ ,  $V_{d2}$  and Q. Final model selection will be based on changes in the objective function and graphically by goodness of fit plots. The final population model will be assessed using bootstrap analysis. MAb114 dosing strategies and their ability to achieve and maintain target MAb114 concentrations will be performed using the final population PK model and Monte Carlo simulations with at least 5000 replicates.

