### 1.1.2 Rationale for Dose and Administration Route Selection

Preclinical data in the NHP animal model informed the doses of MAb114 (5-50 mg/kg) that will be evaluated. In the GLP toxicity study, MAb114 doses ranging from 50 to 500 mg/kg/ week were well-tolerated, with MAb114 demonstrating linear kinetics and a 7-15-day half-life. Preliminary evidence in a NHP model of EVD showed a 50 mg/kg dose of MAb114 was protective to NHPs when administered up to five days post-EBOV challenge [16]. Moreover, a 25 mg/kg dose is important to explore because PK data on a 25mg/kg dose is valuable should future, planned dose-down studies in an NHP dose-down lethal challenge establish protection.

In an epidemic situation, application of effective protection measures against EBOV infection is urgent for exposed individuals. MAb114 will be administered by IV infusion to accelerate delivery as passive immunization studies with other MAbs developed by the VRC has shown antibody concentration peaks within hours after IV administration [21].

Refer to the Investigator's Brochure (IB) for more information on these proof-of-concept preclinical studies.

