#### 4.2.5 Pharmacokinetics

PK samples will be collected as close as reasonably possible to the target timepoints. Because the time of blood collection is critical for PK analysis, the actual time of the phlebotomy will be recorded for all samples. The PK target timepoints are defined in the Schedule of Evaluations (Appendix III).

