#### 4.4 Criteria for Discontinuing Study Participation

A subject may be discontinued from study participation for the following reasons:

1. Subject decides to discontinue participation;
2. Subject develops a medical condition that is a contraindication to continuing study participation;
3. The IND sponsor or regulatory authority stops the study;
4. The PI (or designee) assesses that it is not in the best interest of the subject to continue participation in the study or that the subject's compliance with the study is not sufficient.

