#### 6.4.6 Interim Analyses

Preliminary PK analyses may be performed once per dose level as the data for each dose level is obtained. This will be used to inform decisions about the dose levels to be administered in studies that may begin while VRC 608 is still in progress.

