**Footnotes:**

 Physical exam: If medically indicated, a targeted exam is performed. Otherwise only blood pressure, pulse and temperature are required.

 Pregnancy test and pregnancy prevention counseling are required at visits as indicated for women of reproductive potential.

 Human leukocyte antigen (HLA) type blood sample: If the HLA type within 2 years is not available in the medical record, a blood sample will be collected once. HLA type may also be obtained from a frozen sample.

 PK samples: PK draws may be cancelled at Visits 15 and 16 if results from Visit 14 are available and show no detectable MAb114, however these visits will still be required.

† ADA assessed from serum samples as indicated. Banked serum from any study visit may also be used for ADA assessment.

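### Section 6.4.5: linear trapezoids put NCA AUC about 2-6% high, and tying C_last to Week 24 leaves AUC and its tail undefined for a subject whose sampling ends early

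*Combined protocol and SAP*

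**What the plan says.** Section 6.4.5 (Individual Subject PK Analysis) lists AUC and CL among the NCA parameters and summarises them by dose group. AUC up to C_last "will be determined using the linear trapezoidal method", where C_last "is the concentration at 24 weeks after the dose". The tail has the same anchor: if the final sample, which the text labels C_last, "has measurable MAb114 concentrations, the remaining AUC after the final concentration" is estimated as C_last/λz.

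Other sections allow the Week 24 value to be absent:

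- Appendix III (continued), footnote 4: "PK draws may be cancelled at Visits 15 and 16 if results from Visit 14 are available and show no detectable MAb114".
- Section 4.4 gives "Subject decides to discontinue participation" as one reason for leaving the study.
- Section 6.4.6: "Preliminary PK analyses may be performed once per dose level as the data for each dose level is obtained". It gives no cut date and does not say whether the method is NCA.

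Section 4.2.5 says that "the actual time of the phlebotomy will be recorded for all samples", so the time of any last sample is known. No section gives an AUC endpoint or tail rule for a subject without a Week 24 concentration.

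**The concern.** There are two separate issues.

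First, a straight line between two points on a convex falling curve lies above the curve. Every interval after the end of infusion therefore adds a small excess to AUC, and CL (dose/AUC) comes out low.

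Second, both the endpoint and the tail depend on one sample 24 weeks after dosing. For a subject who leaves early, or in a preliminary NCA run before Week 24, the analyst must choose an endpoint and decide whether to extrapolate after seeing the data. PK at each dose level is a secondary objective (Section 3.2) and the planned groups have 3, 5 and 10 subjects, so one subject handled differently can move a group summary.

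**Working it through.** **Inputs from the documents.** Sampling times (Appendix III): end of infusion, 1, 3 and 6 h, Days 1, 2, 7, then weekly to Day 56, then Days 84, 112, 140 and 168. A two-compartment shape is expected (Section 6.4.5). Half-life: "MAb114 demonstrating linear kinetics and a 7-15-day half-life" (Section 1.1.2), from the primate toxicity study. The documents state no AUC or CL figure to reproduce.

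**Assumptions.** C(t) = f·exp(-λa·t) + (1-f)·exp(-λz·t), with f = 0.3, 0.4 or 0.5, distribution half-life 1, 1.5, 2 or 3 days, and terminal half-life 7, 10 or 15 days, or 20, 24 or 28 days as an assumed longer range. Day 28 and Day 56 are illustrative exit times.

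**One curve by hand** (f = 0.4, half-lives 2 and 15 days).

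- AUCinf = (0.4×2 + 0.6×15)/0.693 = 9.8/0.693 = 14.14.
- To Day 168: true 14.13; linear 14.51 (+2.7%); log-down 14.24 (+0.7%).
- Share beyond Day 28: 0.6×15×2^(-28/15)/9.8 = 9×0.274/9.8 = 25.2%.
- Linear AUC to Day 28 with no tail: 10.80, against a true 10.58. Net CL error = 14.14/10.80 - 1 = +31%.

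With a terminal half-life of 7 days the two errors nearly cancel: the omitted share is 4.2×2^(-4)/5.0 = 5.3%, linear AUC to Day 28 is 7.14 against AUCinf of 7.21, and CL is off by +1%.

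**Full grid, noise-free.**

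| Quantity | 7-15 d | 20-28 d (assumed) |
|---|---|---|
| Linear AUC to Week 24 | +2.2% to +5.6% (median +3.4%) | +1.5% to +2.6% |
| Log-down AUC to Week 24 | +0.4% to +1.8% | +0.3% to +0.9% |
| AUCinf omitted, Day 28, no tail | 4.4% to 26.7% | 33.0% to 49.2% |
| AUCinf omitted, Day 56, no tail | 0.3% to 7.3% | 12.5% to 24.6% |

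With full follow-up at 7-15 days, CL is low by 1 - 1/1.022 = 2.2% to 1 - 1/1.056 = 5.3%.

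Net CL error with early exit (linear to the last sample, no tail):

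- Day 28: about 0% to +2% at 7 days, +9% to +13% at 10 days, +27% to +34% at 15 days.
- Day 56: slightly negative at 7-10 days (down to -5%), +4% to +6% at 15 days.

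At 15 days, the Day 28 exit leaves that subject's AUC short by 1 - 1/1.27 = 21% to 1 - 1/1.34 = 25%. Dividing by n = 3, that subject alone moves the group mean AUC by about 7-8%.

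**Effect of the fix with noise.** Assumed lognormal assay error, CV 20%, exit at Day 28, 7-15 days, λz from the last three points. Flag: more than 20% of AUC extrapolated, or λz not estimable.

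| AUC error | Without fix | With fix |
|---|---|---|
| All subjects, median absolute | about 12% | about 7% |
| All subjects, 5th-95th percentile | about -30% to +9% | about -15% to +29% |
| Unflagged only, 5th-95th percentile | about -25% to +10% | about -15% to +14% |

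About 27% of subjects are flagged overall, and about 68% at a 15-day half-life. At Day 56 the median absolute error falls only from 6.0% to 5.5%.

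**The case against.** The linear trapezoid is a recognised, prespecified rule, and log-down still leaves up to +1.8%. The study is primarily descriptive (Section 6.3.1) and sets no AUC or CL threshold. Early exit is hypothetical: no withdrawal rate is given, and subjects must be available through the last visit. Section 6.4.6 only permits preliminary PK and does not name NCA. Much of this stands and is why the priority is limited. It does not supply the missing rule.

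Four stronger readings are tempting but unsupported:

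- *Footnote 4 loses material AUC.* Cancellation requires an undetectable Week 16 sample. Under assumed assay limits of 0.1-2 mcg/mL and volumes of 40-60 mL/kg, the AUC beyond the last quantifiable sample has a median of 0.7%. The maximum is 2.0% at 25 and 50 mg/kg and 8.6% at 5 mg/kg. Adding no tail also fits the evident sense of the plan.
- *Dose-group comparisons are distorted.* The linear bias depends on half-life, not dose, so it is alike across groups with similar half-lives.
- *Half-life or the dosing simulations are wrong.* Half-life comes from λz, and the simulations use the population model. Neither uses this rule.
- *The fix cleanly narrows the error.* Setting unflagged subjects with the fix against all subjects without it would suggest so, but flagging removes the hardest profiles. Like for like, across all subjects, it exchanges underestimation for a longer upward tail.

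**Conclusion.** Both parts hold, at low to moderate priority. The linear rule puts AUC to Week 24 about 2-6% high at 7-15 days and 1.5-2.6% high at an assumed 20-28 days; log-down cuts this to 0.3-1.8%. The Week 24 anchor matters only when sampling ends early, through withdrawal or through a preliminary NCA if one is run before Week 24. On the most literal fallback (last sample, no tail), the net CL error at 7-15 days is about 0% to +34% at Day 28 and -5% to +6% at Day 56. That fallback is one reading, since the plan states none.

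The sizes rest on an assumed bi-exponential shape and on a primate half-life; the documents give no human half-life, assay limit or assay CV. The direction of the linear bias and the absence of a rule do not depend on those assumptions.

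**What to change.** In Section 6.4.5:

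- use linear-up/log-down trapezoids;
- define C_last as the last quantifiable concentration, at its actual sampling time;
- add C_last/λz from that point when λz is estimable, stating the minimum number of points;
- report each subject's percentage of AUC extrapolated, and flag AUCinf and CL above a prespecified limit (20% in the check above is an assumption);
- apply the same rule to any NCA under Section 6.4.6.

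The cost is a few sentences and a software setting, with no extra samples or visits. The plan should acknowledge the downside: with short follow-up, extrapolation from three noisy points can overshoot, and at a 15-day half-life most Day 28 exits would be flagged. Summaries with and without flagged values would show this openly.

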#### 6.4.6 Interim Analyses

Preliminary PK analyses may be performed once per dose level as the data for each dose level is obtained. This will be used to inform decisions about the dose levels to be administered in studies that may begin while VRC 608 is still in progress.

### 7. PHARMACY PROCEDURES

The study groups and study product dosing schedule are shown in **Table 3**. Refer to the IB for further information about the investigational study product and administration regimen.

#### 7.1 Study Product and Administration Regimen

The study includes an investigational monoclonal antibody described as follows:

- VRC-EBOMAB092-00-AB (MAb114)

In this study, the amount of antibody needed for dosing is based on subject weight and treatment group assigned. In calculating the dose to administer, it should be assumed that the concentration of reconstituted MAb114 is 50 mg/mL, and that a volume of at least 8 mL can be withdrawn from a vial.

For example, if a subject is 80 kg, the volumes for clinical dosing per infusion would be as follows:

- If an 80 kg subject enrolled in Group 1 (5 mg/kg), 400 mg (8 mL) should be administered
- If an 80 kg subject enrolled in Group 2 (25 mg/kg), 2000 mg (40 mL) should be administered
- If an 80 kg subject enrolled in Group 3 (50 mg/kg), 4000 mg (80 mL) should be administered

Preparation of MAb114 for IV administration will require 0.9% sodium chloride, USP (normal saline). For all groups, normal saline (100 mL preferred) and weight-based amount of reconstituted MAb114 will be added to a sterile empty bag (250 mL preferred).

#### 7.2 Study Product Storage

The product label designates the long-term storage temperature as 2-8°C. The site pharmacist must promptly report any storage temperature excursions to the IND sponsor's authorized representative (Appendix II). The affected product must be quarantined in a separate area. The IND Sponsor's authorized representative will notify the site pharmacist if continued clinical use of the product is acceptable.

### 7.3 Preparation of Study Product for Administration

This section describes how the site pharmacist will prepare the study product for administration and how the clinician will administer the product.

Preparation is to be done in a limited access, biological safety cabinet with laminar flow using aseptic technique. During preparation, the pharmacist should assure that only the required vials are present in the preparation unit, and medication labels are strictly segregated to avoid mix-ups.

The following instructions apply to preparing the product for infusion:

1. Calculate the total amount of MAb114 (mg) needed based on the subject's weight and assigned dose level.
2. Remove vial(s) from storage and equilibrate to room temperature for at least 20 minutes
3. Add 7.7 mL of SWFI to each vial
4. Gently mix the vial by swirling, stopping every 30 seconds to let the vial sit on the counter for 10 seconds, until reconstitution is complete. Reconstituted product should be a clear, light yellow liquid, essentially free of visible particles. It may take up to 30 minutes to achieve a completely clear (particle free) solution. If particles are still observed in a vial, the vial should not be used for product administration.

Reconstituted or diluted drug product will be maintained for no more than 4 hours at room temperature or 24 hours at 2°-8°C prior to administration.

More information on product preparation can be found in the IB.

It is expected that each vial will be used for the 8 mL withdrawal volume (400 mg of MAb114); however, more may be withdrawn if it is possible to do so. For each IV infusion order, the subject's weight and dose level will be included in the pharmacy order.

To prepare an IV infusion, the pharmacist will fill an empty sterile bag (250 mL preferred) with normal saline (100 mL preferred), calculate the total amount of MAb114 (mg) needed, reconstitute the minimum number of vials needed to obtain the full dose and add the calculated total mg needed to the sterile bag filled with normal saline (100 mL preferred) using good pharmacy practices to maintain sterility.

An in-line filter infusion set must be used for all IV product administrations. The pharmacist should add the in-line filter to the tubing and prime the set prior to delivery to the clinical setting. In-line filters must comply with the following specifications: 1.2 micron PES (polyether sulfone) filter membrane, DEHP-free, latex-free.

The IV bag prepared by the pharmacy will include the total amount (mg) of MAb114 added to normal saline in an empty sterile bag, and an in-line filter infusion set.

Before beginning the IV administration, the clinician responsible for administration and another clinician will each check the bag label and verify the identifier, the dosage level, that the total amount of product to be administered is correct based on the subject's weight, and that the filter is in place.

The investigational study product solution will typically be administered by IV infusion for approximately 30 minutes, based on factors such as subject tolerance, using a volumetric pump. Longer infusion times will be allowed if clinically warranted.

## 7.4 Labeling of Study Product

Vials of study product will be individually labeled with the name of the material, lot number, concentration, storage instructions, Investigational Use Statement (“Limited by Federal Law to Investigational Use”), and manufacturer information.

## 7.5 Study Product Accountability

The study pharmacist will be responsible for maintaining an accurate record of the codes, inventory, and an accountability record of study product supplies. Electronic documentation as well as paper copies may be used.

## 7.6 Study Product Disposition

The empty vials and the unused portion of a vial will be discarded in a biohazard containment bag and incinerated or autoclaved after use. Any unopened vials that remain at the end of the study will be returned to the production facility or discarded at the discretion of the sponsor in accordance with policies that apply to investigational products. Partially used vials will not be administered to other subjects or used for *in vitro* experimental studies. These vials will be disposed of in accordance with institutional or pharmacy policy.

# 8. HUMAN SUBJECT PROTECTIONS AND ETHICAL OBLIGATIONS

This research study will be conducted in compliance with the protocol, International Council for Harmonisation’s Good Clinical Practice (ICH-GCP) guidance, and all applicable regulatory requirements.

## 8.1 Informed Consent

The study informed consent form (ICF) is provided in Appendix I. It describes the study product to be used and all aspects involved in protocol participation.

The PI or designee is responsible for obtaining written informed consent from each subject after adequate explanation of the aims, methods, anticipated risks and benefits of the study and before any protocol-specific procedures are conducted or the study product is administered. The AoU will be completed before the study ICF is signed.

The acquisition of informed consent will be documented in the subject’s medical records, as required by 21 CFR 312.62. The ICF will be signed and personally dated by the subject, the person who conducted the informed consent discussion, and a witness. The original signed ICF will be retained in the medical chart and a copy will be provided to the subject.

## 8.2 Risks and Benefits

### 8.2.1 Risks

MAb114: There is no prior human experience with administration of MAb114.

MAbs: Administration of MAbs may cause immune reactions such as acute anaphylaxis, serum sickness and the generation of antibodies. However, these reactions are rare and more often associated with MAbs targeted to human proteins or with the use of murine MAbs that would have

a risk of human anti-mouse antibodies [24]. In this regard, because MAb114 is targeted to a viral antigen and is a human MAb, it is expected to have a low risk of such side effects.

Typically, the side effects of MAbs are mild to moderate and may include fever, chills, rigors, nausea, vomiting, pain, headache, dizziness, shortness of breath, bronchospasm, hypotension, hypertension, pruritus, rash, urticaria, angioedema, diarrhea, tachycardia or chest pain. Clinical use of MAbs that are targeted to cytokines or antigens associated with human cells may be associated with an increased risk of infections [24]; however, this is not expected to be a risk for a MAb targeted to a viral antigen.

Published experience with human MAbs directed against the cell surface targets on lymphocytes shows that infusion of a MAb may be associated with cytokine release, causing a reaction known as cytokine release syndrome (CRS) [25]. Most infusion-related events occur within the first 24 hours after beginning administration. Severe reactions, such as anaphylaxis, angioedema, bronchospasm, hypotension and hypoxia, are infrequent and more often associated with MAbs targeted to human proteins or with non-human MAb, such as a murine MAb [24]. CRS reactions most commonly occur within the first few hours of beginning infusion and with the first MAb infusion received. This is because the cytokine release is associated with lysis of the cells targeted by the MAb and the burden of target cells is greatest at the time of the first MAb treatment. With licensed therapeutic MAbs, CRS is managed by temporarily stopping the infusion, administering histamine blockers and restarting the infusion at a slower rate [26]. Supportive treatment may also be indicated for some signs and symptoms. Delayed allergic reactions to a MAb may include a serum sickness type of reaction, which is characterized by urticaria, fever, lymph node enlargement, and joint pains. Symptoms may not appear until several days after the exposure to the MAb. This type of reaction is noted to be more common with chimeric types of MAb [24]. In general, and with due consideration of the needs dictated by individual subject symptoms and treating clinician discretion, immediate and delayed reactions to study product would be managed according to the principles of the American Academy of Allergy, Asthma, and Immunology guidelines established in the Drug Allergy: Practice Parameters (2010).

Participation in this study may limit a subject's eligibility for future MAb studies.

**Risks of Blood Drawing:** Blood drawing may cause pain and bruising and, infrequently, may cause a feeling of lightheadedness or fainting. Rarely, it may cause infection at the site where blood is taken. In this study, an IV line that can be used for blood collection may be placed in the arm and left in place for several hours on Day 0 for frequent PK blood draws. Problems from use of an IV for blood drawing are generally mild and may include pain, bruising, minor swelling or bleeding at the IV site and rarely, infection, vein irritation (phlebitis), or blood clot.

